## Study objectives

---

- 1) To evaluate the effect of a deprescribing-specific interdisciplinary quality circle module on the use of potentially inappropriate medication in nursing-home residents.
- 2) To determine the effective strategies to reach and implement deprescribing consensus resulting of said quality circle module.

## Outcomes

---

### Primary outcome

The overall proportion of galenic units considered inappropriate (possibly and probably inappropriate) will be computed for each NH using the following formula:

$$\frac{\text{(total number of inappropriate galenic units used during the period)}}{\text{(total number of galenic units used during the period)}}$$

The difference between baseline and 12 months will then be computed for each NH.

### Secondary outcomes

Difference in proportion of probably inappropriate galenic units and of possibly inappropriate galenic units: the baseline to 12-month difference in the proportion of possibly inappropriate drugs and of probably inappropriate drugs will be computed for each NH using the same method as for the primary outcome.

Difference in proportion of probably inappropriate DDDs and of possibly inappropriate DDDs: for each data line, the number of DDDs will be computed by multiplying the number of galenic units with the number of DDD per galenic unit. The latter is present in the database used created by the CPC for the monitoring of the cantonal PAPs. The change in proportion of possible inappropriate DDDs and probably inappropriate DDDs will then be computed as for the primary outcome.

Number of hospital days per mean resident and per year: for each year, NH will report the total number of days spent in the hospital (i.e. days spent outside of the NH for medical reasons). The total number of days spent in the NH will be provided by the CPC monitoring team; the mean number of days in hospital per year and per mean resident will then be computed using the following formula:

$$(total\ number\ of\ days\ in\ hospital)/(total\ number\ of\ days\ spent\ in\ NH)/365$$

Mortality rate: NH will report the number of residents having died during each year. The annual mortality rate will then be computed for each NH using the following formula:

$$(total\ number\ of\ deaths)/(total\ number\ of\ days\ spent\ in\ NH)/365$$

Number of falls per mean resident and per month: for each year, NH will report the number of falls. The monthly number of falls per mean resident will then be computed for each NH using the following formula:

$$(total\ number\ of\ falls)/(total\ number\ of\ days\ spent\ in\ NH)/365$$

Number of restraints measures per mean resident and per month: for each year, NH will report the number of restraint measures episodes enacted. The number of falls per mean resident and per year will then be computed for each NH using the following formula:

$$(total\ number\ of\ restraint\ measures\ episodes)/(total\ number\ of\ days\ spent\ in\ NH)/365$$

## Statistical analysis

---

The treatment groups were randomly allocated among nursing-homes (NH). The analyst will be blinded with regard to the allocation.

Analyses will be performed at NH level, the NH being the unit of analysis (i.e. there is one data point per NH per variable).

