5.3 Procedures

For clarity, the following section only describes activities planned for the first recruitment round. If a second round is necessary (see above), all activities will be held the following year in the NHs participating in this second round.

Randomisation:

Some responsible physicians work in multiple NHs; this could lead to contamination of the control group. Moreover, some NHs have multiple responsible physicians; these two factors lead to the apparition of clusters of physicians working in the same NHs and which could amplify contamination of the control group. To account for this factor, after inclusion and before randomisation, NHs will be clustered by physicians: all NHs sharing at least one physician will be placed in the same cluster. NHs sharing no physician with another will be placed in clusters of size one.

A random list of A (intervention) and B (control) will be used to allocate NHs clusters to groups. The list will be constructed by generating a random list of numbers comprised between 0 and 1, with uniform distribution; numbers below 0.5 will be assigned the letter A, the others the letter B. The list will be of the same length as the list of included NHs clusters, and will be generated using Stata version 14.1.

Given the variable size of the clusters, this may lead to the constitution of two groups of unequal size. However, given the relatively small size of expected clusters (the largest possible cluster we are aware of regroups eight NH; most clusters will only include two NHs), this should not lead to a dramatic unbalance between the two groups.

Intervention:

Pharmacists of the NHs assigned to the intervention group will take part in a course where the material for the quality circle module (slides, relevant scientific literature and guidelines) will be made available to them. The content of the course was developed at the CPC. It comprises an overview of the problems posed to older people by polypharmacy and the use of PIMs, an in-depth description of the process of deprescribing and of the challenges to enacting it, a selection of useful clinical tools, and a selection of guidelines to deprescribe specific therapeutic classes (for example, proton-pump inhibitors or cholesterol-lowering drugs).

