In the two months following course completion, every NH in the intervention group will hold a QC session prepared by the pharmacist based on the course. This session will address both generalities about polypharmacy, PIMs and deprescribing, and an in-depth discussion of the guidelines for deprescribing therapeutic classes selected by the pharmacist on the basis of their use in the NH. It is to be noted that the data necessary to select the specific therapeutic classes discussed during the session are both routinely collected and analysed by the NHs' pharmacists, due to their participation in their respective cantonal pharmaceutical assistance programme.

At the end of the session, participants will be required to build a consensus for deprescribing specific therapeutic classes in the NHs. This consensus will then be enacted by the care team, according to their best clinical knowledge. In addition, the participants will be encouraged to think about the strategies to implement each deprescribing measures chosen for the consensus. Physicians will retain complete control over therapeutic choices for individual residents, including the choice to enact the consensus or not.

In addition, the pharmacist will be required to send the consensus with strategies to the other participants two weeks after the session, to include a specific chapter about deprescribing in their PAP annual report for 2017 and to discuss the implementation of the consensus during the presentation of this report to the NH team.

All consensus and implementation strategies chosen by the participating NHs will be collected by the investigators, compiled and, after anonymization, communicated to the participants during the first trimester of 2018.

Data collection:

Assessment of this project's outcomes will be made using anonymised data, provided by the CPC monitoring team. These data will comprise, for every NH and every year:

- Mission of the NH (geriatric, psycho-geriatric, or mixed);
- Number of beds in the NH;
- Mean age of NH residents;
- Gender repartition of the residents;
- Total number of days spent at the NH;

- Total number of days sent in the hospital;
- Total number of deaths in the NH;
- Designation, pharmacode, number of boxes and total cost of every drug used in the NH during the year.

Some data will be collected directly in the NHs; these data will be aggregated at the NH level:

- Total number of falls in the NH;
- Total number of residents having fallen, if available;

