5.4 Methods of minimising bias

To account for the other influences on the prescribing practices of physicians, a controlled design has been chosen. Thus, external influence from medical literature, expert opinions, treatment guidelines or other sources should equally impact NHs in the intervention and control groups.

Randomisation will increase the likelihood that the characteristics of participating NHs are similar between the two groups. To account for the fact that some physicians are responsible for more than one NH, thus allowing for "bleeding" of the intervention between the two groups, randomisation will be clustered at the physician level (see section 5.3, page 13 for details).

Previous discussions with the prospective participants and their professional associations show that there is a great interest for deprescribing among partners. We fear that a purely controlled design will prevent the participation of some of the most interested NHs, thus minimising the effect of the intervention. To reduce this risk, we will offer the possibility to participants randomized to the control group to enact the intervention one year after the start of the study. At this point, all NH in the intervention group will have submitted to the intervention and its effects will have full deployed.

Finally, assessments of the study outcomes will be conducted while maintaining allocation blinding, ensuring that no analysis bias occurs.

Given that the unit of analysis is the NH, the risk of loss to follow-up is deemed inexistent. Data collection will take place in the same way as it already routinely does in a satisfactory way, thus reducing the risk of missing data.

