8.3 Planned analysis

Descriptive statistics

Participating NH will be described, by group, in terms of number of beds, mean age of residents, mission (geriatric, psycho-geriatric or mixed), and number of nurses, physicians and pharmacists. Each implementation outcome (list available in Annex 1) will be presented with a suited summative data.

Inferential statistics

The main outcome is the difference in the overall proportion of PIMs used in the NH 12 months after intervention, relative to baseline. The primary analysis will test the difference in the overall proportion of PIMs between the intervention and control groups using a generalised linear regression model, taking the difference in overall proportion of PIMs at 12 months as the dependant variable, and the group allocation (binary variable) and baseline overall proportion of PIMs as independent variables (two-sided α = 0.05). The analysis will be made immediately after the completion of follow-up data collection.

The same analysis will be carried out for the co-primary outcome, with the overall number of potentially inappropriate DDD at 12 months as dependent variable, adjusted for baseline value, taking into account the group allocation.

Generalised linear models will also be used to assess differences in secondary outcomes between the two groups will be tested with the same method as the primary outcome, taking the baseline value and the group allocation as the independent variables, with two-sided $\alpha = 0.05$. If enough supplementary data on falls and hospitalisations are available (see section 7.3 page 19), they will be analysed as the number of falls, respectively the number of hospital days, per mean resident and per year.

All analyses will be made using the Stata statistical package (StataCorp LP, College Station, TX, USA).

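### Clusters of NHs linked by shared physicians are randomised, but every planned model treats NHs as independent, so the 5% error rate is not assured.

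*SAP*

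**What the plan says.** **Randomisation.** Under protocol 5.3 (Randomisation), "all NHs sharing at least one physician will be placed in the same cluster", and a random A/B list with one entry per cluster "will be used to allocate NHs clusters to groups". On cluster size it says: "the largest possible cluster we are aware of regroups eight NH; most clusters will only include two NHs". NHs that share no physician form clusters of one. Section 5.4 repeats that "randomisation will be clustered at the physician level", because a physician responsible for several NHs could carry the intervention across arms.

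**Analysis.** Protocol 8.3 models the change in PIM proportion with "the group allocation (binary variable) and baseline overall proportion of PIMs as independent variables" and nothing else, and applies the same approach to the co-primary and secondary outcomes. The SAP (Statistical analysis) describes the allocation with the words "The treatment groups were randomly allocated among nursing-homes (NH" and does not mention physician clusters. It continues: "Analyses will be performed at NH level, the NH being the unit of analysis". Its inferential section plans least squares adjusted for baseline, a robust variance if variances differ, a GLM if the outcome is not normal, and an unadjusted Mann-Whitney test as last resort. Three count-type secondary outcomes start from a Poisson GLM. None of these carries a cluster term.

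**The concern.** The unit that was randomised is not the unit that the models treat as independent. One row per NH deals with residents clustered within an NH. It does not deal with NHs clustered by physician.

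Correlation between linked NHs is plausible from the protocol's own reasoning. Physicians are expected to carry practice between their NHs (5.4), and they keep control over treatment, "including the choice to enact the consensus or not" (5.3, Intervention). Because a cluster goes to one arm as a whole, positive correlation adds variance to the between-arm contrast that the planned standard error does not see. The p-value of the primary test would then be too small and its confidence interval too narrow.

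Three features limit the correlation. A cluster can be a chain in which some NHs share no physician. An NH may have several physicians. Change scores with baseline adjustment also remove much of any stable shared prescribing style. What remains is shared change during follow-up.

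**Working it through.** **The plan's own figure.** Protocol 8.1 asks for 33 NHs per group (difference 4.6 points, SD 7.5, α 5%, power 80%). The independent-observations formula gives n = 2 × (1.645 + 0.842)² × 7.5² / 4.6² = 32.9, so 33. The figure therefore contains no design effect. (It reproduces with a one-sided 5% only, which is a separate point.)

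**Inputs.** From the documents: 62 NHs (synopsis), clusters mostly of two, one possible cluster of eight, two-sided 5%. Assumed, because the documents do not give them: the ICC of the baseline-adjusted change and the cluster-size distribution.

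**Formulas.** With cluster sizes m:
- design effect DE = 1 + (Σm²/Σm − 1) × ICC
- actual type I error = 2 × [1 − Φ(1.96/√DE)]

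**Layouts (62 NHs each) and analytic error of the nominal 5% test**

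| Layout | Σm²/Σm | ICC 0.05 | ICC 0.1 | ICC 0.3 | ICC 0.5 |
|---|---|---|---|---|---|
| A: one of 8 + 27 pairs | 172/62 = 2.774 | 6.0% | 7.1% | 11.3% | 15.4% |
| B: 31 pairs | 124/62 = 2.000 | 5.6% | 6.2% | 8.6% | 11.0% |
| C: one of 8 + 14 pairs + 26 singletons | 146/62 = 2.355 | 5.8% | 6.6% | 9.8% | 13.0% |
| D: 15 pairs + 32 singletons | 92/62 = 1.484 | 5.3% | 5.6% | 6.7% | 7.9% |

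Example, layout B at ICC 0.3: DE = 1 + 1 × 0.3 = 1.3; √1.3 = 1.140; 1.96/1.140 = 1.719; error 8.6%.

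From D to A, √DE is 1.024-1.085 at ICC 0.1 and 1.070-1.238 at ICC 0.3. The planned standard error is thus too small by about 2-8% and 7-19%.

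**Simulation of the planned baseline-adjusted least squares.** No treatment effect, SD 6.3, ρ 0.3, coin-flip allocation of clusters, 4,000 replicates per cell (Monte Carlo SE about 0.34 points at 5%):

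| Layout | ICC 0 | 0.05 | 0.1 | 0.3 | 0.5 |
|---|---|---|---|---|---|
| A | 5.2% | 5.7% | 7.2% | 10.4% | 14.6% |
| B | 5.1% | 5.7% | 5.8% | 8.4% | 11.9% |
| C | 4.9% | 5.2% | 6.7% | 8.9% | 12.1% |
| D | 5.0% | 5.6% | 5.8% | 6.6% | 7.9% |

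The Mann-Whitney fallback behaves alike: 6.7% (A) and 5.0% (D) at ICC 0.1; 10.5% and 6.4% at ICC 0.3.

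A separate simulation with 66 NHs and ρ 0.54 agrees: 33 pairs give 6.4% and 8.8% at ICC 0.1 and 0.3, and one cluster of eight plus 29 pairs gives 7.2% and 10.9%.

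**Cluster-aware methods in the 62-NH simulation**, all layouts, ICC 0 to 0.5:
- cluster-robust SE with small-sample correction (CR2, Satterthwaite df): 4.5-5.8%
- random cluster intercept (REML, t on clusters − 2 df): 3.9-5.4%
- permutation of clusters: 4.6-5.6%

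In the 66-NH simulation, ordinary cluster-robust SEs with t on clusters − 1 df gave about 5.0-6.7%, so the small-sample correction is needed.

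**The case against.** The omission itself is not in dispute. The case against concerns its size and reach.

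- **Two rounds.** Protocol 5.2 allows a second round that is randomised separately, so NHs linked across rounds may land in opposite arms, where positive correlation makes the planned standard error too large. This stands as a qualification: linked NHs are sure to share an arm only within a round. When clusters were split over two separately randomised rounds, the excess shrank but did not reverse on average (4.9-5.7% at ICC 0.1, 5.6-8.4% at ICC 0.3).
- **Mechanism.** If the intervention does nothing in any NH, a physician's decision to enact it cannot create correlation; only shared drift in prescribing can. This is right for that strict null. If effects vary by physician around a mean of zero, the error also rises (5.6-6.9% at an assumed effect SD of 3 points).
- **Extreme layouts.** Layout A needs all eight linked NHs to enrol, and A and B contain no singletons. Suppose the 124 eligible NHs (82 + 42, protocol 8.1) were one cluster of eight plus 58 pairs, each NH enrolling independently with probability one half. Then Σm²/Σm is about 105/62 = 1.69, and the error is 5.4%, 5.8% and 7.5% at ICC 0.05, 0.1 and 0.3. This is a fair lower-end picture, although enrolment needs the physician's approval, so linked NHs would tend to enrol together.
- **High ICCs.** Nothing in the documents supports 0.3 to 0.5 for a baseline-adjusted change. Those columns are stress values.
- **Other outcomes.** Only the continuous change score was simulated. Small-sample behaviour in the Poisson and other GLMs is untested, and for falls and restraint use the shared-physician argument is weaker.

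**Conclusion.** The concern holds. Clusters are randomised, no planned analysis accounts for them, and the SAP misstates the unit of allocation. These are facts of the text.

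The consequence is conditional. With zero within-cluster correlation the planned test holds 5%. With ICC 0.05 to 0.1 the analytic error is 5.3-7.1% over the four assumed layouts. At ICC 0.3 it is 6.7-11.3%, with the upper end requiring an intact eight-NH cluster. Since the documents give neither ICC nor cluster sizes, the size of the excess is unknown and may be small, but the validity of the primary test cannot be demonstrated as planned. For the co-primary outcome the point rests on protocol 8.3 alone, because the SAP does not contain that outcome.

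**What to change.** 1. Reword the SAP's allocation sentence to say that clusters of NHs sharing physicians were randomised.
2. Add the randomisation-cluster ID, in coded form, to the analysis file. It must already exist, because clusters are formed before randomisation.
3. Keep one row per NH and the baseline covariate. Account for the cluster in every between-arm model, including the co-primary outcome, by one method fixed before unblinding. Either use cluster-robust standard errors with a small-sample correction, which also covers unequal variances and can be applied to the GLM and Poisson models, or use a random cluster intercept with small-sample degrees of freedom.
4. Replace the Mann-Whitney fallback with a permutation test that re-randomises clusters.
5. If a second-round NH shares a physician with a first-round NH, give both the same cluster ID for the variance estimate. The permutation test should follow the clusters as actually randomised in each round.

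The cost is SAP wording and one variable, with no new data. The downside is wider intervals: from layout D to layout A, the median corrected cluster-robust interval in the simulation was wider than the planned one by 1-3% at ICC 0, 3-11% at ICC 0.1 and 8-23% at ICC 0.3.

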## Data preparation

The data of 2017 and 2018 will be pooled for the analysis.

Data will be transferred to the statistician in an Excel spreadsheet and then imported into the Statistical package Stata (StataCorp LLC, College Station, Texas, USA). All data preparations and analyses will be performed on Stata.

The presence of missing values will be checked and the number of missing values quantified for each variable.

The overall proportion of galenic units considered inappropriate (primary outcome) will be calculated with the formula above. The probability distribution of the difference between

baseline and 12 months (primary outcome) will be checked by means of a histogram and the calculation of skewness and kurtosis. If normality cannot be assumed, data will not be transformed (see Data analysis). The same will be done for all the secondary outcomes listed above.

## Descriptive analysis

All descriptive statistics will be reported separately for the two study groups.

The overall proportion of galenic units considered inappropriate will be described at baseline and 12 months by its mean, standard deviation (SD), median, interquartile range (IQR), minimum and maximum values. The same statistics will be reported for the difference between 12 months and baseline.

The very same procedure will be applied to describe the proportion of probably inappropriate galenic units and of possibly inappropriate galenic units (two variables), and the proportion of probably inappropriate DDDs and of possibly inappropriate DDDs (two variables) plus these variables' differences between baseline and 12 months.

The same statistics will be calculated for: number of hospital days/mean resident/year; mortality rate; number of falls/mean resident/month; number of restraint measures/mean resident/month. These variables have no longitudinal structure.

NH population will be described by the number of residents, sex ratio, and mean resident age.

## Inferential analysis

The analysis will follow the intention to treat approach. However, it is expected that all NH comply with the intervention group they have been randomized into.

No formal statistical tests will be applied to compare NH groups for the variables measured before randomization.

If the primary outcome follows a normal distribution and variances between intervention groups are equal, NH groups will be compared by means of linear least-square regression under adjustment for baseline. In case of heteroscedasticity, a robust estimation of the variance will be applied. If the outcome does not follow a sufficiently normal distribution, a generalised linear model (GLM) will be applied with the most appropriate distribution and link function. Residual diagnostics will be used to check the quality of the statistical model. If it is not possible to find an acceptable model, the two NH groups will be compared by means of a Mann-Whitney test without baseline adjustment.

The same procedure will be used to compare the differences between baseline and 12 months for the proportion of probably inappropriate galenic units and of possibly inappropriate galenic units (two variables), the proportion of probably inappropriate DDDs and of possibly inappropriate DDDs (two variables) and for mortality rate.

The number of hospital days/mean resident/year, number of falls/mean resident/month; and number of restraint measures/mean resident/month, being counts, are likely to follow a Poisson distribution. Therefore, a GLM with family Poisson and logarithmic link function will be applied first.
